5.3.3. Instructions to the Subjects before Dosing at Dosing Visit

- (1) No food will be allowed for 10 hours prior to dosing and until 4 hour post-dose PK samples have been collected.
- (2) Meals will be provided at normal times after the 4 hour post-dose blood draw.
- (3) Water intake is not allowed 1 hour before and 1 hour after drug administration.
- (4) All physical activities during the Dosing Visits should be limited with the exception of bathroom visits until the completion of the 120-minute post-dose PK sampling at each Dosing Visit.
- (5) The subject will remain in a semi-recumbent or seated position for 120 minutes after drug dosing. After the 120-minute PK sampling, the subject has no movement restrictions, but should refrain from any excessive physical activity.
- (6) During each Dosing Visit, subjects should refrain from alcohol consumption and caffeine-containing (including decaffeinated) beverages or foods (coffee, tea, applicable soft drinks including cola and analogs, or chocolate).

5.3.4. Study Medication Administration

At each dosing visit, subjects will either self-administer 2 actuations from the MDI inhaler provided, or receive an IM injection (0.30mg Epinephrine injection for Treatment-B).

IM Injection into the vastus lateralis site:

IM injection (0.30mg of epinephrine solution in 0.30 mL) for Treatment-B will be given on the thigh. Subjects will be lying down in a supine position. The 0.30 mL dose will be given perpendicularly as a single deep IM injection into anterolateral aspect of the thigh (vastus lateralis site). Refer to [Section 4.5.4](#) for detailed IM injection procedure.

MDI Self-Administration:

The designated unblinded dispenser at the study site will prime each unit prior to the first use ([Section 4.5](#)). Each subject will also be retrained on the use of the MDI inhalation aerosols as described in [Section 4.5.1 to Section 4.5.3](#).

Study drugs will be dispensed by the designated site professional, and the reading on the dose indicator of the MDI unit will be recorded prior to dosing.

Subject will **shake the inhaler well before each spray**. Subjects will self-administer 2 inhalations from the inhaler unit (within 30 seconds interval between each inhalation). The study drug administration process will be video-recorded and used for an investigation of apparent dosing irregularity. Refer to [Section 4.5.3](#) for critical instructions for correct dosing techniques.

The study medication administration should be conducted between 07:00 and 11:00 AM on the Dosing Visit. Time of the start of each inhalation will be recorded.

Once dosing is completed, CRC or other site professionals will record the readings of each dose-indicator in the study source documents. The used MDI inhaler will be collected at the end of the Dosing Visit.

5.3.5. PK Blood Sampling

At each Dosing Visit, PK blood samples will be collected and plasma will be isolated for analyzing the concentrations of Albuterol, and epinephrine. A total of 26 blood samples will be drawn from each subject at each Dosing Visit as indicated in **Table 2**.

- (1) A catheter will be inserted into one of the antecubital region veins for blood sampling. Alternatively, collection from a vein of the hand or forearm for easier access or via venipuncture is also acceptable;
- (2) One (1) pre-dose samples (baseline) will be collected within 30 minutes before dosing;
- (3) Time 0 is defined as the beginning of the last inhalation of the MDI, or after completion of IM injection, [Section 4.5.3](#).

Table 2. PK Blood Sampling Schedule

Seq. #	Scheduling	Time window	Sample No., "XX"	Seq. #	Scheduling	Time window	Sample No., "XX"
1	Baseline	within 30 min pre-dosing	01	14	40 min		14
2	1 min		02	15	50 min		15
3	2 min	± 0.5 min	03	16	60 min	±5 min	16
4	3 min		04	17	70 min		17
5	5 min		05	18	80 min		18
6	7 min	±1 min	06	19	90 min		19
7	9 min		07	20	120 min	±10 min	20
8	12 min		08	21	4 hrs		21
9	15 min	±1 min	09	22	6 hrs	±15 min	22
10	18 min		10	23	8 hrs		23
11	21 min		11	24	12 hrs		24
12	25 min	±2 min	12	25	18 hrs	±20 min	25
13	30 min		13	26	24 hrs		26

- (4) A catheter flush will be performed between each blood sample collection to avoid catheter clot formation and prevent interference between samples. At each sampling point, the first 1.0 mL portion of the blood (or saline flush) will be collected into a disposable tube and discarded;
- (5) At each PK sampling point, blood samples (~5 mL), will be collected in ice-chilled potassium-EDTA sample tubes, mixed well (gently invert the tube 8-10 times) immediately following collection, kept on ice or refrigerated and centrifuged within 20 minutes of collection.
- (6) If a tube breaks, a new sample can be collected if it is within the allowed time window (**Table 2**).
- (7) Plasma isolation (i.e., centrifugation of the blood samples) will start within 20 minutes of blood collection. Blood samples will be centrifuged at 4°C, 2,000-3,000 g for 20 minutes for plasma isolation.
- (8) Isolated plasma will be distributed into two (2) 2 mL cryo vials, approximately 1.5

mL in the first vial and the remainder in the second vial. The plasma sample vials will be frozen immediately on dry ice (within 60 minutes following plasma separation) and then stored (within 60 minutes following plasma separation) in a freezer at -20°C or lower until analysis.

5.3.6. PK Blood Sample ID and Labeling

The sample ID for PK blood samples (before centrifugation) is defined as

“EIPK-nn-V-XX”

Where, **EIPK-nn** is the subject ID; **V** is the Dosing Visit code, V=1, 2 or 3; and **XX** is the two-digit time-point sequential number of the sample: 01, 02, 03... 26 as listed in **Table 2**.

The sample ID for PK plasma samples (after centrifugation) is defined as “**EIPK-nn-V-XX-k**” and **k** is the aliquot number (A or B). The PK plasma sample ID labels, with the size of 1/2”×1¾” (Avery label 5667), should be printed in blue font as demonstrated below:

EIPK-nn-V-XX-k

5.3.7. Safety Evaluations/Monitoring

The following safety measurements will be performed during each Dosing Visit:

- (1) Vital signs (HR, SBP/DBP): at baseline, 5±2 min, 15±5 min, 60±5 min, 120±15 min and 24 ±2 hrs post-dose.
- (2) 12-lead ECG (routine QT and QTc analysis): at baseline, 20±5 min, 120±15 min and 24 ±2 hours post-dose.
- (3) Serum potassium and glucose levels will be measured at baseline, 10±2 min, 60±5 min, and 24 ± 2 hrs post-dose.
- (4) All subjects will be queried for adverse events (AEs) and AEs must be recorded with all related information.

5.4. Activity at End of Study (EOS)

The following EOS evaluations will be conducted at the end of study as follows:

- (1) The Investigator(s) will ensure that all study drugs and study records are accountable.
- (2) At Visit-3, blood and urine samples will be taken for fasting comprehensive metabolic panel (Refer to [Appendix IV](#)). Lunch will be provided **after** the EOS

blood draw. The meals and fasting schedule is indicated in **Table 3**.

Table 3. Meals and fasting schedule

	Night before Dosing	Day 1	Day 2 (Visit-3 Only)
Morning	NA	Dosing	Breakfast will be provided after EOS blood draw
Mid-Day	NA	Lunch (≥ 4 hr post-dose)	NA
Evening	Dinner, then fast overnight (≥ 10 hr)	Dinner, then fast overnight (≥ 8 hr)*	NA

* At Visit-3, breakfast will be provided after EOS blood draws

- (3) Conduct EOS physical examination between 16 and 26 hours post-dose. EOS Vital signs, ECG, CBC, fasting comprehensive metabolic panel and serum potassium/glucose will be measured at the end of PK sample collection (24 ± 2 hrs post-dose) at Visit-3.
- (4) Adverse events, whether reported by the subjects or observed by study staff, will need to be documented, and reported or **followed up** where applicable.
- (5) Review all safety and compliance data.
- (6) For Early Termination (ET), an ET evaluation will be conducted with the same safety assessments as listed (items 1-5 above) when appropriate and feasible.

5.5. Follow-up Activities

All treated subjects will be followed up by a phone call scheduled 1-7 days after the completion of Dosing Visit-3 or study termination. Subjects will be asked if they have experienced any adverse event after the last Dosing Visit.

5.6. PK Sample Transfer and Laboratory Analysis

The plasma samples will be transferred at temperature below -20°C from the site to the Amphastar R&D Laboratory. The chain of custody, temperature control and related documents for sample transfer must be recorded and documented.

All plasma samples should be stored at -80°C or lower in the laboratory. Epinephrine and Albuterol concentration in the PK plasma samples will be analyzed by the R&D Department of Amphastar with validated methods under GMP.

5.7. Summary and Schema of Study Activities

5.7.1. Data collection

Data collection for this study is summarized as follows:

- PK samples for evaluation of plasma epinephrine or Albuterol concentrations;
- Safety data as vital signs, ECG, urinalysis, serum potassium, glucose and clinical laboratory testing, etc.; and
- Adverse events reported.

5.7.2. Schema of Study Activities

A schematic outline of the study activities is provided in **Table 4** below.

Table 4. Summary of Activities in All Visits and EOS

[figure not shown]
Study Activities & Evaluations	Screen Visit	Dosing Visit-1	Dosing Visit-2 and 3	EOS¹
Informed Consent / HIPAA	X			
Medical history / demographics	X			
Physical Exam (PE)	X			X
Lab: Urinalysis (UA)	X			X
Lab: CBC/Comp. metab. Panel	X			X
Lab: Thyroid Function	X			
Lab: HIV-Ab, HB-sAg, HCV-Ab	X			
Inclusion/Exclusion	X	X		
Confirmation of enrollment		X		
Assign subject ID		X		
Randomization		X		
Training/Dosing of MDI	X	X	X	
Concomitant Medicines		Record throughout study period		
Urine or serum pregnancy test	X	X	X	
Urine drug screen	X	X	X	
Alcohol screen (urine or breathalyzer)	X	X	X	
Food / beverage restrictions		X	X	
Meals served		X	X	
PK Baseline samples		X(1)	X (1)	
PK samples		X (25)	X (25)	
Vital signs	X	X (6)	X (6)	X ²
12-lead ECG	X	X (4)	X (4)	X ²
Serum potassium and glucose	X	X (4)	X (4)	X ²
Adverse event reporting		Record throughout study period		

1. The fasting comprehensive metabolic panel (≥ 8 hours) for EOS will be taken at the Study Visit-3 or study termination
2. Vital signs, ECG and serum potassium and glucose at 24 ± 2 h at Visit-3 can be used for EOS

5.8. Chart for Study Activities

Study activities are summarized in **Figure 1**.

Figure 1. Summary of Study Activities

6. STATISTICAL ANALYSIS

6.1. *Populations*

6.1.1. Per-Protocol Population (PPP)

The “Per Protocol” population is defined as all subjects who have received all study medications during the study and are evaluable for all treatments. The primary analyses will be performed based on “Per Protocol” population (PPP).

An evaluable subject for primary analyses of this study must meet all of the following ten (10) items for both treatments:

- (1) Correct dose and administration;
- (2) Nineteen (19) or more of 25 post-dose PK data points (>75%) are available;
- (3) There are no more than four (4) consecutive missing PK data points;
- (4) The baseline PK data point is available;
- (5) For Treatment-A, at least four (4) of the five (5) PK data points at 1, 2, 3, 5, and 7 minutes post-dose are available;
- (6) For Treatment-B, at least four (4) of the five (5) PK data points at 9, 12, 15, 18, and 21 minutes post-dose are available;
- (7) For Treatment-C, at least four (4) of the five (5) PK data points at 25, 30, 40, 50, and 60 minutes post-dose are available;
- (8) For Treatment-A, at least three (3) of the PK data points at 25, 30, 40, and 50 minutes post-dose are available.
- (9) For Treatment-B, at least three (3) of the PK data points at 80, 90, 120 minutes and 4 hours post-dose are available; and
- (10) For Treatment-C, at least three (3) of the PK data points at 6, 8, 12 and 18 hours post-dose are available.

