4. CALCULATION OF RELATED STATISTICAL QUANTITIES

4.1 PK/PD PARAMETERS

4.1.1 Primary Endpoints

(1) C_{max} , in units of pg/mL, is defined as the maximum of experimental data points of epinephrine or albuterol concentration for a given subject and given treatment:

[figure not shown]
$$C_{max} = \max (C_1 \cdots C_i \cdots C_n) \quad i = 1, 2, 3 \cdots n \quad (1)$$

where C_i is the observed plasma concentration of albuterol or epinephrine at the time t_i ; which is the sampling point time;
 t_1 is the baseline, and n is the number of available PK measurements.

(2) $AUC_{0-t_m}^{Tot}$ for Total API,

As is demonstrated in the left plot of **Figure 1**, the AUC is for total API, including both exogenous and endogenous, if the endogenous active ingredient exists, such as epinephrine for Treatments A and B.

Figure 1 AUC for Total Active Ingredient (left) and Drug Exposure (right)

$AUC_{0-t_m}^{Tot}$ is reported in units of pg/mL*hr, can be calculated per the trapezoidal rule as given the Eq. (2):

$$AUC_{0-t_m}^{Tot} = \sum_{i=1}^{m-1} \frac{C_i + C_{i+1}}{2} (t_{i+1} - t_i) \quad (2)$$

where

- t_m is the time of the first PK point for the subject and the treatment, after C_{max} , that is reduced to the same day baseline (C_0), if C_0 is detectable, such as for epinephrine, (see **Fig. 1**, left plot); and
- $t_m > t_{max}$, and is the smallest time point that meets

$$C(t_m) \leq C_0 + \frac{1}{2} QL \quad (3)$$

- $t_m = 24$ hrs for albuterol, or m is the number of available PK measurements until t_m .

(3) The AUC for Drug Exposure $AUC_{0-t_m}^{DE}$

The AUC for the drug exposure, as is demonstrated in the right plot of **Figure 1**, is the AUC for exogenous API, if the endogenous active ingredient exist such as epinephrine for Treatments A and B.

$AUC_{0-t_m}^{DE}$ is reported in units of pg/mL*hr, and is calculated as follows:

$$AUC_{0-t_m}^{DE} = AUC_{0-t_m}^{Tot} - C_0 t_m \quad (4)$$

where $AUC_{0-t_m}^{Tot}$ and t_m is obtained based on Eqs. (2) and (3).

(4) **Drug Exposure $AUC_{0-\infty}$** (in units of pg/mL*min) is defined as below

$$\begin{cases} AUC_{0-\infty} = AUC_{0-t_m}^{DE} & \text{if } t_m < 24 \text{ hrs} \\ AUC_{0-\infty} = AUC_{0-t_m}^{DE} + AUC_{t_m-\infty}^{DE} & \text{if } t_m = 24 \text{ hrs} \end{cases} \quad (5)$$

$AUC_{t_m-\infty}$ can be obtained per the extrapolation method as given in the Eqs. (6) –(7) below, based on the time is long enough so that

$$C(t) \approx Be^{-k_e t}, \quad (6)$$

thus

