5.2.1 Missing Data Handling for Evaluable Subjects

For an evaluable subject that was defined in Section 5.1.1, only a small portion of PK measurements, if any, are allowed to be missed, and the interpolation method will be used for imputation.

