1	C2-C4 (Min. 1,2,3): 1 ± 0.5	1	0.5 min	0%	0%	0 min	0	-	no flag allowance
2	C5-C7 (Min. 5,7,9): 2 ± 1	2	1 min	0%	0%	0 min	0	-	ibid
3	C8-C11 (Min. 12, 15, 18, 21): 3 ± 1	3	1 min	50%	0%	0 min	0	-	ibid
4	C12-C13 (Min. 25,30): 5 ± 2	5	2 min	25%	25%	0.5 min	0.5	100%	
5	C14-C19 (Min. 40, 50, ...80, 90): 10 ± 5	10	5 min	0%	0%	0 min	0	-	no flag allowance
6	C20-C21 (hr. 2): 120 ± 10	30	10 min	50%	0%	0 min	0		ibid
7	C20-C21 (hr. 4): 120 ± 10	120	10 min	500%	50%	5 min	30	17%	
8	C22-C23 (hr. 6,8): 120 ± 15	120	15 min	300%	300%	45 min	45	100%	
9	C24-C26 (hr. 12, 18,24): 360 ± 20	360	20 min	800%	300%	60 min	40	150%	

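### The evaluability rule limits missing samples by count and not by time, so an IM profile with a 16-hour gap can be evaluable and its epinephrine AUC overstated (low severity)

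*Protocol*

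**What the plan says.** Protocol 6.1.1 and SAP 5.1.1 carry the same ten evaluability items. Four bear on this point.

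- Item (2), total count: "Nineteen (19) or more of 25 post-dose PK data points (>75%) are available".
- Item (3), runs: "There are no more than four (4) consecutive missing PK data points". The limit is a number of samples.
- Item (9), late phase of Treatment B: "For Treatment-B, at least three (3) of the PK data points at 80, 90, 120 minutes and 4 hours post-dose are available; and". The samples at 80, 90 and 120 min satisfy it without 4 h.
- Item (10) protects the late samples for albuterol only: "For Treatment-C, at least three (3) of the PK data points at 6, 8, 12 and 18 hours post-dose are available". Treatments A and B have no requirement beyond 50 min and 4 h respectively.

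SAP 4.1.1 computes the epinephrine AUC by the linear trapezoid (Eq. 2) over the available points up to t_m. That is the first time after the peak at which the concentration is at or below C0 + 1/2 QL; the SAP says it "and is the smallest time point that meets" Eq. (3). Eq. (4) subtracts the baseline. Eq. (5) takes the result as AUC0-infinity whenever t_m is before 24 h. SAP 5.2.1 says that in evaluable subjects a small portion of measurements "are allowed to be missed, and the interpolation method will be used for imputation", without giving the scale. SAP 5.3.2.3 divides AUC0-infinity of A by that of B within each subject and averages the ratios.

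**The concern.** Sampling is dense early and sparse late. Four consecutive samples span minutes near the peak and many hours later on. After 4 h, SAP Table 4 lists "C22-C23 (hr. 6,8): 120 ± 15" and then "C24-C26 (hr. 12, 18,24): 360 ± 20". A limit of four missing samples therefore permits a gap from 120 min to 18 h, or from 4 h to 24 h.

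Item (9) treats 80 min to 4 h as informative for Treatment B, which suggests that some excess over baseline is expected at 120 min. If so, a straight line to the next sample counts area that was never observed as injected epinephrine. Treatment B is the denominator of RBA, so the error makes inhaled exposure look smaller relative to injection. Treatment A is less exposed: item (8) places its late phase at 25-50 min, and protocol 1.4 cites inhaled epinephrine back at baseline 20 min after a much larger dose. The error would therefore tend to run in one direction.

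**Working it through.** **The plan's own figure.** 19/25 = 76%, and 18/25 = 72%. Nineteen is the smallest count above 75%, as item (2) states.

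**Does the gap pass?** Treatment B with 4, 6, 8 and 12 h missing:

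| Item | Requirement | This profile |
|---|---|---|
| (2) | at least 19 of 25 | 25 - 4 = 21 |
| (3) | at most 4 in a row missing | 4 |
| (4) | baseline present | present |
| (6) | 4 of 5 at 9-21 min | 5 |
| (9) | 3 of 4 at 80, 90, 120 min, 4 h | 3 |

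With the dose correctly given (item 1), it is evaluable. A profile missing 6, 8, 12 and 18 h (gap 4 h to 24 h) also passes. Under Treatment C both patterns fail item (10).

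**Size of the tail.** Let E be the excess over baseline at 120 min, above 1/2 QL.

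- 4 h present and at baseline: t_m = 4 h, tail = (4 - 2) x E/2 = 1E.
- 4 and 6 h missing, 8 h at baseline: tail = (8 - 2) x E/2 = 3E.
- 4-12 h missing, 18 h at baseline: t_m = 18 h, tail = (18 - 2) x E/2 = 8E. Since 18 < 24, Eq. (5) carries this unchanged into AUC0-infinity.
- 6-18 h missing, with excess E4 at 4 h still above 1/2 QL: tail after 4 h = (24 - 4) x E4/2 = 10 E4, against (6 - 4) x E4/2 = 1 E4 when 6 h is present and at baseline.

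Let A2 be the baseline-corrected AUC from 0 to 2 h. The 16 h gap doubles the AUC when A2 + 8E = 2(A2 + E), that is, when E = A2/6 per hour.

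**What E might be.** This needs assumptions. I used a noise-free one-compartment IM profile peaking at 15 min, with C0 = 0.23/1.50 x 275, about 42 pg/mL, from protocol 1.4 (C0 cancels in Eq. 4). I applied Eqs. (2)-(4) with the full schedule and then with samples removed. For a peak of 200 pg/mL above baseline and QL 10 pg/mL, with 4-12 h missing:

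| Half-life | AUC, gap / full | Subject's RBA multiplied by |
|---|---|---|
| 20 min | 1.32 | 1/1.32 = 0.76 |
| 30 min | 1.69 | 1/1.69 = 0.59 |
| 40 min | 1.97 | 1/1.97 = 0.51 |
| 60 min | 2.16 | 1/2.16 = 0.46 |

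With only 4 and 6 h missing, the same half-lives give 1.09-1.27.

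Over a peak of 100-400 pg/mL, QL 5-20 pg/mL and half-life 15-60 min:

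| Missing | Inflation of B's AUC |
|---|---|
| 4 h | 0-17% |
| 4 and 6 h | 0-34% |
| 4, 6, 8 and 12 h | 0-128% |

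The zeros are cases where 120 min is already at or below C0 + 1/2 QL. Doubling needs a half-life of about 40 min or more.

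**Study level.** With equal RBAs, one halved subject among 24 gives (23 + 0.5)/24 = 0.979, a fall of 2.1%. Three give (21 + 1.5)/24 = 0.9375, a fall of about 6.3%.

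**The case against.** The strongest reply is that the pattern is contrived. It needs 4, 6, 8 and 12 h all missing and 18 h present. A subject who leaves after 120 min also loses 18 and 24 h, which makes six in a row, and item (3) already excludes that profile. Subjects check in the night before, meals wait for the 4 h draw, and another vein or venipuncture may be used. The causes of missing data listed in protocol 6.2.3 are mostly single-sample events. This stands, and it is why the severity is low.

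The size is also uncertain. Protocol 1.4 describes IM epinephrine as short-acting, and with a short half-life the effect is small or nil. In the 20 min case above, E is about 7.5 pg/mL, so QL 20 pg/mL would remove the effect. If a linearly imputed point may serve as t_m, which the SAP does not settle, that case falls from x1.32 to x1.17. Interpolation on the log scale would reduce the inflation but not remove it. All of this stands.

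The analysis is descriptive: no test, margin or acceptance limit applies to RBA. Missing samples are tabulated and individual curves plotted, so a long straight line would be seen. Seeing it does not correct Eq. (2), and a decision taken then would be made after the data are known.

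A reader might infer that the Treatment B denominator is generally doubled, or that the trial's RBA is materially biased. The documents support neither. Doubling is conditional on assumed kinetics and applies to one subject's value. The protocol's AUC0-6h is less sensitive (about x1.04-1.36 over a somewhat wider set of assumptions), and SAP 2.1 replaces it with AUC0-t.

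**Conclusion.** The defect in the rule follows from the text: a Treatment B profile with no sample from 120 min to 18 h, or from 4 h to 24 h, is evaluable. If the last sample before the gap is still raised, the SAP's equations overstate that subject's AUC and understate its RBA. The documents cannot fix the size. On the assumptions above it is 0-128% in the extreme pattern and 0-17% when only 4 h is lost. Because the pattern is unlikely and one affected subject moves the mean RBA by about 2%, this is a low-severity correction, worth making because it is cheap and can be settled before the data are seen.

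**What to change.** In protocol 6.1.1 and SAP 5.1.1, add an item: every Treatment B profile, whatever its concentrations, must have at least two of the 4, 6 and 8 h samples. Together with item (9), this keeps any gap that starts before 6 h to about 4 h. If 4 h is missing, the gap is 120 min to 6 h; if 6 h is missing, it is 4 h to 8 h. The remaining inflation is then of the order of the 0-17% found with 4 h alone missing.

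In SAP 5.2.1, state that interpolation is not used across a longer gap before t_m and that t_m must be a measured point. Profiles that fail are handled under the existing non-evaluable rule (SAP 5.2.2).

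A tempting alternative is to drop the AUC only when 120 min is still raised and keep Cmax and tmax. I advise against it. It would selectively remove slow-eliminating, high-AUC Treatment B profiles and push RBA upward. Evaluability by parameter would also conflict with the all-treatments per-protocol definition and with SAP 5.2.2.

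The cost is a few sentences in two documents, no added sampling, and the occasional loss of a subject from the per-protocol PK analysis.

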6.1.2. Treated Population (TP)

The “treated” population is defined as all subjects who have been randomized and treated with any dose of the study drugs.

The safety evaluation will be performed base on treated population (TP).

6.1.3. Intent-to-treat Population (ITT)

The “Intent-to-Treat” population is defined as all subjects who have been randomized.

